1.3.1 Rationale for the Trial and Selected Subject Population

Based on this accumulated data, we propose a Phase II trial to evaluate the safety and efficacy of pembrolizumab followed by PET-directed combination chemotherapy, for patients with previously-untreated cHL. We propose evaluation of patients with stage I-IV disease including elderly patients.

Elderly patients have poor tolerance and outcomes with standard chemotherapy. By specifically assessing the elderly cohort, we hope to improve the efficacy and tolerability of frontline therapy in a group that otherwise employs a disparate prognosis. In this group bleomycin will be omitted, and pembrolizumab will be given both prior to AVD, as well as following AVD as consolidation. In the young cohort, we predict that the increased efficacy of pembrolizumab added to AVD will improve rates of CR as assessed on interim FDG-PET, and thus reduce the total number of patients requiring radiation therapy. By avoiding radiation in this cohort we hope to reduce the rates of late effects of therapy and second malignancies. Our strategy of administering anti-PD-1 therapy upfront prior to chemotherapy will allow us to assess the rates of CR on PET-CT scan which will further increase our understanding of the prognostic significance of PET-CT scans with this novel class of agents in HL.

1.3.2 Rationale for Dose Selection/Regimen/Modification

An open-label Phase I trial (Protocol 001) is being conducted to evaluate the safety and clinical activity of single agent MK-3475. The dose escalation portion of this trial evaluated three dose levels, 1 mg/kg, 3 mg/kg, and 10 mg/kg, administered every 2 weeks (Q2W) in subjects with advanced solid tumors. All three dose levels were well tolerated and no dose-limiting toxicities were observed. This first in human study of MK-3475 showed evidence of target engagement and objective evidence of tumor size reduction at all dose levels (1 mg/kg, 3 mg/kg and 10 mg/kg Q2W). No MTD has been identified to date. Recent data from other clinical studies within the MK-3475 program has shown that a lower dose of MK-3475 and a less frequent schedule may be sufficient for target engagement and clinical activity.

PK data analysis of MK-3475 administered Q2W and Q3W showed slow systemic clearance, limited volume of distribution, and a long half-life (refer to IB). Pharmacodynamic data (IL-2 release assay) suggested that peripheral target engagement is durable (>21 days). This early PK and pharmacodynamic data provides scientific rationale for testing a Q2W and Q3W dosing schedule.

A population pharmacokinetic analysis has been performed using serum concentration time data from 476 patients. Within the resulting population PK model, clearance and volume parameters of MK-3475 were found to be dependent on body weight. The relationship between clearance and body weight, with an allometric exponent of 0.59, is within the range observed for other antibodies and would support both body weight normalized dosing or a fixed dose across all body weights. MK-3475 has been found to have a wide therapeutic range based on the melanoma indication. The differences in exposure for a 200 mg fixed dose regimen relative to a 2 mg/kg Q3W body weight based regimen are anticipated to remain well within the established exposure margins of 0.5 - 5.0 for MK-3475 in the melanoma indication. The exposure margins are based on the notion of similar efficacy and safety in melanoma at 10 mg/kg Q3W vs. the proposed dose regimen of 2 mg/kg Q3W (i.e. 5-fold higher dose and exposure). The population PK evaluation revealed that there was no significant impact of tumor burden on exposure. In addition, exposure was similar between the NSCLC and melanoma indications. Therefore, there are no anticipated changes in exposure between different indication settings.

The rationale for further exploration of 2 mg/kg and comparable doses of pembrolizumab in solid tumors is based on: 1) similar efficacy and safety of pembrolizumab when dosed at either 2 mg/kg or 10 mg/kg Q3W in melanoma patients, 2) the flat exposure-response relationships of pembrolizumab for both efficacy and safety in the dose ranges of 2 mg/kg Q3W to 10 mg/kg Q3W, 3) the lack of effect of tumor burden or indication on distribution behavior of pembrolizumab (as assessed by the population PK model) and 4) the assumption that the dynamics of pembrolizumab target engagement will not vary meaningfully with tumor type.

The choice of the 200 mg Q3W as an appropriate dose for the switch to fixed dosing is based on simulations performed using the population PK model of pembrolizumab showing that the fixed dose of 200 mg every 3 weeks will provide exposures that 1) are optimally consistent with those obtained with the 2 mg/kg dose every 3 weeks, 2) will maintain individual patient exposures in the exposure range established in melanoma as associated with maximal efficacy response and 3) will maintain individual patients exposure in the exposure range established in melanoma that are well tolerated and safe.

A fixed dose regimen will simplify the dosing regimen to be more convenient for physicians and to reduce potential for dosing errors. A fixed dosing scheme will also reduce complexity in the logistical chain at treatment facilities and reduce wastage.

1.3.3 Rationale for Endpoints

Efficacy Endpoints

Our primary endpoint is to assess rate of complete response following pembrolizumab alone. Among those patients whose disease has failed frontline treatment, as well as treatment with brentuximab vedotin (BV), pembrolizumab has shown dramatic activity, with a 53% overall response rate (ORR), 20% rate of CR, and disease regression in 14 of 15 patients³⁷. We predict an improvement in CR rate of 50% to pembrolizumab alone as assessed by PET-CT prior to initiation of chemotherapy among patients treated in the frontline setting.

Exploratory Studies

The mechanism of suppression of the anti-tumor response is well understood for the PD-1 pathway^{36,38}. Utilization of PD-1 blockade in solid malignancies has revealed changes in the T-cell lymphocytic subset consistent with on-target effects of anti-PD-1 agents³⁹. Prior clinical trials for the PD-1 inhibitor, nivolumab, included correlates investigating biomarkers of response. Correlative studies in participating patients demonstrated copy-number gains in PDL1 and PDL2 and increased expression of these ligands. Reed-Sternberg cells showed nuclear positivity of phosphorylated STAT3, indicative of active JAK-STAT signaling. Interestingly, tumor infiltrating T- cells expressed low levels of PD-1 on immunohistochemical analysis. Overall, levels of PD-1 expression were not significantly predictive of response, in contrast to studies in solid tumors, where this seems to be more predictive of response. The author's postulated PD-1 blockade may selectively enhance the function of CD8+ T cells with low levels of PD-1 expression.

In addition to PD-1 and PD-L1 expression, multiple lines of evidence support the evaluation of different biomarkers for patients with cHL treated with PD-1 blockade. Serum receptors/cytokines CD30, CCL17, and CCL22, may have prognostic value with respect to PFS and OS among patients with cHL⁴⁰. Moreover, CD8+ T-cell density, along with PD-1+ and PD-L1+ tumor/T-cell expression/density, may predict for activity of pembrolizumab⁴¹,⁴². And clinical data have shown that PD-1 inhibition yield significant increases in number of host PD-L1-bearing activated T-cells⁴³. These data suggest that baseline tumor features, as well as dynamic host features, may be important predictors of response to pembrolizumab. Furthermore, a recent abstract by

18

Moscowitz et al⁴⁴ demonstrated cysteine-cysteine thymus and activation related chemokine (TARC) as a biomarker for response and PET normalization in HL after treatment with BV. This biomarker warrants additional investigation.

2.0 OBJECTIVES & ENDPOINTS

2.1 Primary Objective

Objective: Assess the percent of patients who achieve a complete response (CR) to single-agent pembrolizumab induction, among patients with cHL using Lugano 2014 criteria, as measured at PET#2.

Hypothesis: We hypothesize that frontline pembrolizumab, followed by FDG-PET-directed combination chemotherapy, will produce excellent efficacy. We predict a CR rate of 50% to pembrolizumab alone as assessed by PET-CT prior to initiation of chemotherapy. Furthermore, the addition of standard chemotherapy utilizing an age and stage-adjusted approach will result in an increased number of patients with PET-negativity at interim PET, and the ability to limit the number of cycles of chemotherapy, and further reduce the need for radiation therapy, thereby minimizing acute and chronic toxicity.

2.2 Secondary Objectives

Objective: Assess the safety and tolerability of pembrolizumab in combination with chemotherapy in the frontline setting.

Hypothesis: The combination of pembrolizumab with AVD as frontline treatment will be well tolerated. Furthermore, the addition of standard chemotherapy utilizing an age and stage-adjusted approach will result in an increased number of patients with PET-negativity at interim PET, and the ability to limit the number of cycles of chemotherapy, and further reduce the need for radiation therapy, thereby minimizing acute and chronic toxicity

Objective: Determine the extent of FDG uptake, using a semi-quantitative approach (eg, Deauville score), after pembrolizumab induction, and after subsequent chemotherapy.

Hypothesis: The percentage of patients with a Deauville score of 1-2 after pembrolizumab alone will be 50%. The percentage of patients with a Deauville score of 1-2 following two cycles of chemotherapy will exceed 75%.

2.3 Exploratory Objectives

Exploratory objectives will assess the value of tissue biomarkers as predictors of response to pembrolizumab, including the following:

- To characterize PD-1 pathway specific expression and correlate with response
- To characterize serum biomarkers of immune, inflammatory response and other biomarkers during treatment
- To characterize levels of soluble PD-L1 related to treatment with pembrolizumab
- To characterize T-lymphocyte subset changes to treatment with pembrolizumab
- To investigate the prevalence and clinical correlation of chromosome 9p24.1 alterations for this population
- Assess cysteine-cysteine thymus and activation related chemokine (TARC) as a biomarker for response and PET normalization

Each enrolled patient will provide a fresh tissue biopsy sample if available from the biopsy performed for diagnosis, or an archived sample as agreed upon by the PI for additional marker expression analysis. Peripheral blood will be obtained at specified time points for serum marker analysis.

Initial Version date: March 10th, 2017

Amendment 6: March 29th, 2019

19

PD-1 Pathway Marker Expression

Tissue sample slides from the baseline biopsy will be evaluated by immunohistochemistry for expression of PD-1 and PD-L1 on either malignant cells or within the tumor microenvironment. Samples will be deemed either positive or negative for marker expression. Presence/absence (binary) of PD-1 and PD-L1 will be correlated with response to pembrolizumab and clinical outcomes.

Immune and Inflammatory Markers

Peripheral blood will be tested for serum levels of TNF- α , IFN- γ , IL-2, galectin-1, TGF- β , IL-10, IL-13, and indoleamine 2 3-dioxygenase (IDO). Testing will be performed using commercially available kits. Levels will be compared from specified time points through treatment.

Soluble PD-L1

Peripheral blood obtained at day 1 of cycle #1 then at the off-treatment visit will be analyzed by a commercially available ELISA assay (USCN Life Sciences – product number SEA788Hu). Levels will be compared to evaluate for a change (increase/decrease) following treatment with pembrolizumab.

Lymphocyte Subset Changes

The endpoint is whether or not a patient is a lymphocyte subset responder. Responders are defined as either a) a 50% increase or b) a half standard deviation increase in lymphocyte subsets. Lymphocyte subsets will be evaluated by flow cytometry on peripheral blood obtained at specified time points through the treatment period41-43. Flow cytometry analysis will include the following surface markers: CCR7, CD3, CD4, CD8, CD14, CD16, CD20, CD25, CD45RO, CD56, CD57, CD62L, CD107a, CD127, FoxP3, B7-H1 (PD-L1), B7-DC (PD-L2), HLADR, and PD-1. The following intracellular markers will be evaluated: TIA1, granzyme, perforin. We will complete an 8-10 color flow cytometry analysis to properly group biomarkers for determination of specific lymphocyte populations. Two specific lymphocyte populations will be evaluated: CD4+CD25+PD-L1+ T lymphocytes and CD4+CD62L+CD127+ T lymphocytes. Lymphocyte subsets are continuous measurements in cells/µL.

Chromosome 9p24.1 Alterations

Tissue sample slides from the baseline biopsy will be evaluated by FISH break-apart probes for mutations at chromosome 9p24.1. Presence of amplifications. Frequency and magnitude of 9p24.1 alterations-polysomy, copy gain, and amplification will be determined. We will also assess the association of 9p24.1 alterations with clinical parameters, including stage (early stage I/II favorable risk, early stage unfavorable risk, advanced stage (AS, III/IV) and progression-free survival (PFS), as well as age.

TARC Thymus and Activation-Regulated Chemokine/CCL17 (TARC)

Patients will have TARC assessed prior to therapy utilizing patient's serum. TARC will be measured using a commercially available double antibody sandwich ELISA. Elevation of TARC has been associated with decreased response to chemotherapy and an increased inflammatory environment. We will correlate pre-treatment TARC levels with PET responses and assess for changes in TARC levels after treatment with immunotherapy.

Initial Version date: March 10th, 2017

Amendment 6: March 29th, 2019

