- ¹⁴ PET/CT is required for eligibility within 6 weeks prior to registration (standard of care) and at specified time points for tumor assessment for the primary endpoint analysis. PET#2 should take place prior to starting AVD (research procedure). PET#3 should take place at the end of AVD Cycle 2 (standard of care). Copies of PET/CT scans should be de-identified and CD disks with DICOM files shipped within 30 days for central review as outlined in section 6.3.1.
- ¹⁵ All patients will have a PET/CT 2-6 weeks after the completion of chemotherapy (or diagnostic CT's for patients with Stage I/II disease and a negative PET#3) (standard of care). This will be prior to starting consolidation treatment (when applicable) or as part of the procedures for study discontinuation. Patients receiving consolidation will also have a final PET/CT as part of study discontinuation.
- ¹⁶ For patients who receive pembrolizumab consolidation, imaging is recommended every 3 months. Once a PET-CT is negative, patients may undergo CT's every three months during consolidation.
- ¹⁷ Diagnostic quality CT scan of the chest/abdomen/pelvis is required within 6 weeks prior to registration. If there is involvement of the neck then a diagnostic quality CT Neck is required.
- ¹⁸ Correlative studies on tissue specimens are recommended if there is adequate tissue on the baseline sample acquired for diagnosis. Patients who agree to undergo a repeat biopsy (optional: done as a research procedure) for the interim assessment will provide tissue 2-4 weeks after the first dose of pembrolizumab as specified in the lab manual, however repeat biopsy is not required.
- ¹⁹ See separate lab manual for details of correlative studies (research procedures). Study labs include:
 - (1) sodium heparin tube for FlowCore,
 - (2) SST tube for Inflammatory and Immune Markers,
 - (3) SST tube for Soluble PD-L1
 - (4) SST for CCL17

¹ Treatment cycle of pembrolizumab defined as 21 days, Treatment cycle of AVD defined as 28 days with treatment on days 1 and 15

² Interim assessment by FDG-PET #2 for primary endpoint assessment on day 64 +/- 3 days

³Labs including CBC w/ANC and comprehensive chemistry panel, physician visit with physical examination and vital signs to be performed on day 1 of each cycle of AVD.

⁴ Interim assessment by FDG-PET #3 for PET-directed therapy on day 117-120 prior to AVD cycle 3

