9.2 Biopsy Specimen Analysis

Immunohistochemical stains for PD-1 and PD-L1 will be performed by the Northwestern PathCore facility with proper controls. We will also perform IHC for CD3 and CD20 for identification of tumor cells and the tumor microenvironment. Samples will be reported as "present" or "absence" of marker expression. Expression will be quantified by percentage of cells with differentiation between malignant cell expression and/or tumor microenvironment expression. We will consider >20% as "positive" for PD-1 or PD-L1 expression.

FISH

Fluorescence in situ hybridization (FISH) will be performed by the Northwestern pathology department on tissue sections to assess alterations of chromosome 9p24.1. Chromosomal alterations will be characterized as amplification, copy gain, polysomy, or normal copy number (disomy). The bacterial artificial chromosome probes (CHORI; www.chori.org) RP11-599H2O, which maps to 9p24.1 and includes CD274 (encoding PD-L1, labeled with Spectrum Orange), and RP11-635N21, which also maps to 9p24.1 and includes PDCD1LG2 (encoding PD-L2, labeled with Spectrum Green), will be cohybridized. A control centromeric probe, Spectrum Aqua—labeled CEP9 (Abbott Molecular) that maps to 9p11-q11, will be used. An additional probe, Spectrum-Greenlabeled RP11-6010G2, which maps upstreatm of PDCD1LG2, will be used to confirm a possible chromosomal translocation.

Double Immunohistochemistry Staining

Slides will be double stained for the presence of PD-L1 and PAX5 (24/Pax-5;BD Biosciences, San Jose, CA) as well as PD-L2 clone and pSTAT3 (D3A7; Cell Signaling, Danvers, MA). These stains will be performed with an automated staining system (Bond III; Leica Biosystems, Buffalo Grove, IL). Stained slides will be scored by an expert hematopathologist for average percentage of positive cells and intensity of staining on a scale (1-3+).

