10.3.3 Analytic Plan for Exploratory Objectives

All enrolled patients who receive at least one injection of study drug and have a correlative sample will be included in the exploratory immune biomarker analysis. Tabulation, summarization and descriptive statistics will be performed describing the baseline and post pembrolizumab biomarkers. To assess whether PD-1 and PD-L1 and related pathway expression on paired biopsy samples prior to and following single agent pembrolizumab is related to response, the difference in biomarker expression will be calculated. A signed rank test will determine whether this change is significant and a rank sum test will determine whether the level of biomarker change before and after pembrolizumab is related to response as measured by PET#2. A similar analysis will be done for changes in serum cytokines, markers of immune/inflammatory response changes in lymphocyte subsets by flow cytometry and cysteine-cysteine thymus and activation related chemokine (TARC).

Genetic alterations in chromosome 9p24.1 (amplification, increased copy number, polysomy, and disomy) measured at baseline will be related to response using logistic regression.

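### Baseline PD-1 and PD-L1 are recorded as a percentage of cells but related to response and outcomes only as a yes/no value, at an unexplained and loosely defined 20% cut

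*Combined protocol and SAP*

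**What the plan says.** **Scale of measurement.** Section 9.2 (Biopsy Specimen Analysis): "Expression will be quantified by percentage of cells with differentiation between malignant cell expression and/or tumor microenvironment expression".

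**Classification.** The same section says "Samples will be reported as 'present' or 'absence' of marker expression" and then "We will consider >20% as 'positive' for PD-1 or PD-L1 expression". It gives no source or reason for 20% and does not say which compartment the cut applies to. Section 2.3 (PD-1 Pathway Marker Expression), on the baseline biopsy, says "Samples will be deemed either positive or negative for marker expression".

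**Baseline analysis.** Section 2.3: "Presence/absence (binary) of PD-1 and PD-L1 will be correlated with response to pembrolizumab and clinical outcomes". Section 10.3.3 names no test for this comparison. For baseline values it offers only descriptive statistics, plus a logistic regression for the 9p24.1 alterations.

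**Paired analysis.** For biopsies before and after pembrolizumab, section 10.3.3 says "the difference in biomarker expression will be calculated". That change is tested with a signed rank test, and then "a rank sum test will determine whether the level of biomarker change before and after pembrolizumab is related to response as measured by PET#2". The second biopsy is optional: the tissue footnote in section 5.0 says "however repeat biopsy is not required".

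**The concern.** Section 2.3 opens by giving the exploratory aim as the value of tissue biomarkers as predictors of response. Because the second biopsy is optional, baseline tissue is the main source for that aim, and at most 30 patients will supply it. The plan collects a graded measurement and then discards the grading before the one comparison that uses the baseline value.

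Two problems follow.

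- **Power.** A real association is harder to detect after the cut. If most samples fall on one side of 20%, it may be impossible to detect. A null result could then reflect the cut and not the marker.
- **Definition.** Two analysts working from the same slides could derive different variables. A sample with 10% staining might be coded *present* by one and *negative* by the other. A sample above 20% in the microenvironment but not in malignant cells has no stated code.

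**Working it through.** The plan states no power, alpha, effect size or positive share for any biomarker analysis, so there is no figure of its own to reproduce.

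**1. Is the baseline percentage analysed anywhere?**

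| Place | Quantity | Analysis |
|---|---|---|
| 2.3 | Baseline marker, binary | Correlated with response and clinical outcomes |
| 9.2 | Percentage of cells, by compartment | None stated |
| 10.3.3 | Baseline and post-treatment biomarkers | Descriptive statistics |
| 10.3.3 | Paired change in expression | Signed rank test; rank sum test by PET#2 response |
| 10.3.3 | Baseline 9p24.1 alterations | Logistic regression on response |

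No row relates the baseline PD-1 or PD-L1 percentage to response or outcome.

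**2. What a yes/no marker can show at this sample size.** This step needs no effect size.

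- Inputs: 26 evaluable patients (sections 3.0 and 10.2); 50% CR predicted in 2.1, so 13 responders and 13 non-responders; two-sided Fisher test at 5% (assumed).
- Best case for the hypothesis that positive samples respond more: all *k* negative samples belong to non-responders. With equal groups, p = 2 × C(13,k) / C(26,k).
- k = 4: 2 × 715 / 14,950 = 0.096.
- k = 5: 2 × 1,287 / 65,780 = 0.039.

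At least 5 negative samples are therefore needed. With 22 or more of 26 positive (22/26 = 85%), the test cannot reach p < 0.05 in that direction, however strong the association.

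At 40% CR (about 10 responders and 16 non-responders) the requirement rises to 7:

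- k = 6: [C(16,6) + C(10,6) + 16 × C(10,5)] / C(26,6) = (8,008 + 210 + 4,032) / 230,230 = 0.053.
- k = 7: [C(16,7) + C(10,7) + 16 × C(10,6)] / C(26,7) = (11,440 + 120 + 3,360) / 657,800 = 0.023.

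**3. Illustrative power, by simulation.** Expression and depth of response are bivariate normal; responders are the best 40% by depth; n = 26; two-sided 5%. The correlation and the share positive are assumptions. The 40% CR rate is the plan's sizing alternative (10.2).

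| Test | r = 0.4 | r = 0.5 | r = 0.6 |
|---|---|---|---|
| Rank sum on the percentage | 32% | 50% | 69% |
| Fisher, 50% positive | 19% | 29% | 45% |
| Fisher, 70% positive | 12% | 19% | 30% |
| Fisher, 80% positive | 7% | 10% | 15% |
| Fisher, 90% positive | <2% | <2% | <2% |

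- Loss with Fisher at 50% positive: 32 − 19 = 13, 50 − 29 = 21 and 69 − 45 = 24 points.
- Loss with Fisher at 90% positive: about 32 − 2 = 30 to 69 − 2 = 67 points.
- A repeat run with an uncorrected chi-square test at 50% positive gave rank sum power of 34% to 69% and chi-square power of 27% to 57%. The loss is 34 − 27 = 7 to 69 − 57 = 12 points.
- At 90% positive, chi-square power also stays in single figures, so the large loss there is not produced by choosing Fisher.

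**4. How far the size depends on the inputs.** A second model shifts the responders' marker by d standard deviations (13 v 13, two-sided 5%, formula-based).

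- d = 1.0: power on the continuous scale is 72%; the loss is 23, 37, 49 and 57 points at 50%, 80%, 90% and 95% positive.
- d = 0.5: loss of 8 to 17 points.
- d = 1.5: loss of 13 to 78 points.

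Across all the splits, tests and alpha levels tried, the loss ran from about 0 to over 90 points.

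**The case against.** Several points on the other side stand.

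- **The plan does use the graded scale elsewhere.** A reader might infer that PD-1 and PD-L1 are analysed only as positive or negative throughout. Section 10.3.3 contradicts that, since it applies rank tests to paired change.
- **The paired tests do not collapse.** A reader might also infer that 10.3.3 takes differences of a 0/1 marker, so that its signed rank test reduces to a sign test on the few samples that switch category. No section says so. The binary sentence in 2.3 concerns the baseline biopsy, and the percentages in 9.2 are the natural input to 10.3.3. All that is missing is a statement of the scale.
- **The power loss is not a property of this plan.** It rests on an assumed correlation, share positive, test and alpha. At an even split, using chi-square in place of Fisher removes up to about half of it.
- **A lopsided split is possible but not established.** Section 1.3 describes up-regulation of this pathway. Section 1.3.3, however, reports low PD-1 on tumour-infiltrating T cells in an earlier trial of a PD-1 inhibitor and no significant prediction of response from PD-1 levels. No section gives the share of samples expected above 20%.
- **Power is modest either way.** Tissue is used only where available, so n = 26 may be optimistic. Even the rank sum test has only 32-50% power at correlations of 0.4-0.5.
- **A cut fixed in advance has a merit.** It prevents a threshold from being chosen after the data are seen.

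None of this supplies an analysis of the baseline percentage, a reason for 20%, or a coding rule for 1-20% staining and for the two compartments. A percentage analysed by ranks also leaves no threshold to choose.

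**Conclusion.** The point holds for the baseline analysis. A percentage is recorded by compartment, only a binary form of it is related to response and clinical outcomes, and that form is neither justified nor fully defined.

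The direction of the power loss is secure; its size is not. The illustrative figures are about 7-24 points at an even split (chi-square to Fisher) and about 30-67 points at 90% positive (Fisher). They hold only for n = 26, 40% CR, latent correlation 0.4-0.6 and two-sided 5%. The firmest figure is the count: with a 13/13 response split, Fisher's test cannot reach p < 0.05 in the expected direction with fewer than 5 negative samples. It assumes only the group sizes, the test and the alpha.

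The importance is minor. Section 10.0 describes the biologic correlates as exploratory, and no stopping rule, treatment assignment or primary conclusion depends on these markers.

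**What to change.** - **Section 2.3.** Replace the binary sentence with: *Baseline PD-1 and PD-L1 will be analysed as the percentage of positive cells, separately for malignant cells and microenvironment. Each will be compared by PET#2 response with a rank sum test and related to clinical outcomes as a continuous predictor.* This keeps the clinical-outcome part of the objective.
- **Section 9.2.** Keep >20% as a secondary, descriptive category. Use one term for it, say how 1-20% staining is coded and which compartment the cut applies to, and give the reason for 20% or state that it is arbitrary.
- **Section 10.3.3.** Add the baseline comparison, and state that the paired difference is the difference in percentage of positive cells.

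The cost is wording in three sections. Section 9.2 already requires the percentage, so no new data are needed. Results become slightly less simple to report than a yes/no split, which can still be tabulated. Two markers in two compartments give four response comparisons, which should be presented as exploratory.
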